### **Setting and location**

The first phase of the study, linked to Aim 1, does not involve human subject research. It only involves the study team, key consultants, and expert advisors who will work at their respective institutions.

The phase 2 and 3 studies are conducted from a single site, the School of Nursing at Emory University. We will centrally and via Zoom videoconferencing software (from Emory) consent the organizational leaders, interventionists trained by the system we developed and dementia family caregivers engaged in Savvy Caregiver programs provided by system-trained interventionists to participation in a wait-list design study in which caregivers from each site will be randomly assigned to immediate participation in a Savvy program offered by one of the newly trained interventionists or to delayed participation in Savvy (after 4 months). Each participant will be asked to complete the same post-program participation survey via Zoom videoconferencing software (from Emory) as in the Phase 2 study, and each will be asked to take part in four phone or video interviews in which Emory staff will administer well-established and validated questionnaires to assess burden, depression, anxiety, and caregiver competence and mastery as well as care recipient well-being. As in the phase 2 study, a sub-sample of caregiver participants (N=18) will be asked to participate in semi-structured interviews – also completed via Zoom videoconferencing software - focused on their perceptions of the interventionist's program leadership skills, any adaptation experiences, and on ways in which they met their own needs and expectations. In both phases (2 and 3) organizational leaders and system-trained

interventionists will be asked to take part in qualitative formative evaluation interviews conducted by Emory study staff.

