Results from Savvy participant quantitative fidelity monitoring surveys will be compiled in a simple spread sheet to allow us to see whether there are any notable problems in interventionist performance either within or across sites or in or across interventionists. Likewise, we will be able to compare caregivers' responses about knowledgeability and competence with responses we have received from other caregivers in Savvy programs provided by interventionists who were trained in person by [name] or [name].

Once a cohort of 20 consented caregivers has been formed at any local organization, participants will be assigned (through a random procedure administered by Emory staff) to take part immediately in one of the Savvy programs offered by either of the 2 interventionists or to take part in one of the 2 interventionists' programs after 4 months; follow-up phone or video interviews will be conducted at 2, 4, and 6 months lasting each 1-1.5 hours in length. The audio files from interviews will be saved on Emory School of Nursing's secure share-drive within a password protected folder for 5 years post-study completion.

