## **10. Plans for analysis**

Multi-level mixed effects models (MLM) with random (participant) and fixed (cohort) effects will be employed to test for linear (and non-linear) trajectories of change for the Intervention group versus waitlist

group focusing on the group-by-time effect. To address the primary effect of the Savvy intervention, the Immediate group will be compared to the waitlist delay group, using the first 2 time points (0m-2m) to test for differences between the 2 groups' changes post intervention. Additionally, the combined Savvy intervention effects will be assessed using a paired t-test for the combined immediate group's first 2 time points (0m-2m) with the waitlist delay group's 2 time points before and after beginning Savvy (4m-6m). If there are significant differences between the 2 groups at the time point immediately prior to receipt of the intervention, these "baseline" effects will be included and adjusted for a final analysis of covariance (ANCOVA) model for these change scores. Given that the immediate group will have 3 post-intervention measurements (2m-4m-6m), MLM longitudinal models will also be employed to assess the overall time effects plus planned post hoc comparisons for both the immediate intervention effect and the longer term and sustained effects. Sidak Type-I error rate adjustment (which has higher power than Bonferroni) will be applied for the multiple pairwise time point comparisons. The proposed study design also has the advantage of capturing "baseline" time points for the delay group (0m-2m-4m) which will provide an excellent opportunity to evaluate what if any potential "placebo" effects there may be from being enrolled in this type of study. These initial data captured at 0m-2m-4m for the delay group will also be used to evaluate any potential decline occurring during this time period. All model assumptions will be tested; grand mean centering used to help combat multi-collinearity between variables; and standard diagnostic tests and influence statistics used to test the distributions of the residuals. MLM models utilize all available data for all participants at each time point and have the advantage of adjusting for the missing data over time, where repeated measures ANOVAs do not. Further covariate predictors of missingness (mainly due to attrition) over time will be included to additionally adjust for these confounders SPSS v.24 will be used for all analyses at the 5% significance level.

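### On the 2/4/6-month schedule, lasting benefit is drawn from the immediate arm's own visits, although a randomized 4-month comparison is available and not named

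*Combined protocol and SAP*

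**What the plan says.** Everything on analysis is in section 10, Plans for analysis.

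- **Trajectory model.** Mixed models "will be employed to test for linear (and non-linear) trajectories of change for the Intervention group versus waitlist", with the focus on the group-by-time effect. The visits entering the model are not listed.
- **Primary contrast.** Immediate against delayed, "using the first 2 time points (0m-2m) to test for differences between the 2" groups.
- **Persistence.** The plan notes that "the immediate group will have 3 post-intervention measurements (2m-4m-6m), MLM longitudinal models will also be employed" to assess time effects, together with "planned post hoc comparisons for both the immediate intervention effect and the longer term and sustained effects". The pairwise time-point comparisons are Sidak-adjusted.
- **Delayed arm.** Its 4- and 6-month visits are described as its "2 time points before and after beginning Savvy (4m-6m"). Its visits up to 4 months serve to look for placebo effects, and "These initial data captured at 0m-2m-4m for the delay group will also be used to evaluate any potential decline".

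The documents give more than one interview schedule. Field Methods says "follow-up phone or video interviews will be conducted at 2, 4, and 6 months", and Setting and location says "each will be asked to take part in four phone or video interviews in which Emory staff will administer" the questionnaires, which fits 0/2/4/6 months. Study Design and Recruitment instead give the immediate arm three interviews (0, 3 and 6 months). They give the delayed arm four: at sign-up, just before its program, and two later ones. Those later ones fall 3 and 6 months after program start in Study Design, but 3 and 6 months after program completion in Recruitment.

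**The concern.** Change within a treated arm equals the treatment effect plus whatever would have happened anyway: regression to the mean, the effect of being in a study, or worsening as the dementia advances. The plan intends to look for such drift in the delayed arm, but no step removes it from the persistence estimate. A claim of lasting benefit could therefore reflect drift, or real benefit could be hidden by shared decline. A concurrent randomized comparison at 4 months would avoid this and needs no extra interviews on the 2/4/6-month schedule.

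A secondary point concerns the trajectory model. Two visits cannot support a non-linear trajectory, so the model must reach beyond 0 and 2 months. If it takes in the 6-month visit without a term for Savvy exposure, the delayed arm is already treated there, and the group-by-time term no longer contrasts treated with untreated caregivers throughout.

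**Working it through.** The documents give no effect size, SD, correlation, drift or allocation ratio for these outcomes, so there is no planned figure to reproduce. From the documents: N = 6 x 20 = 120, 5% level, Sidak adjustment. Assumed: 60 per arm, total SD 1, correlation r = 0.6 between any two visits, two-sided tests, no dropout, no clustering.

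**1. Who is treated when (2/4/6-month schedule).** At 2 and 4 months only the immediate arm has had Savvy. At 6 months both have. The last randomized treated-against-untreated comparison is therefore at 4 months.

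**2. Drift in the within-arm estimate.** With effect e and shared drift g, the immediate arm's 0-4 month change is e + g, the delayed arm's is g, and the difference is e.

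Within-arm SE = sqrt(2(1 - r)/n) = sqrt(2 x 0.4/60) = 0.115, with 59 df. Sidak per-pair level = 1 - 0.95^(1/k): 0.0170 for k = 3 pairs and 0.0085 for k = 6. The plan does not give k. Rejection rate with e = 0:

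| Shared drift | Sidak, 3 pairs | Sidak, 6 pairs | Unadjusted 5% |
|---|---|---|---|
| 0.1 SD | 6% | 4% | 14% |
| 0.2 SD | 24% | 17% | 40% |
| 0.3 SD | 56% | 46% | 72% |

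At 0.2 SD drift, moving r from 0.4 to 0.8 (SE 0.141 to 0.082) moves the 3-pair figure from 16% to 50% and the 6-pair figure from 10% to 40%. In 6,000 simulated trials the between-arm change contrast, tested at 5%, rejected 4.9%, 5.2% and 4.5% of the time for the three drifts.

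Drift can also hide benefit. With shared worsening of 0.2 SD, a true 0.5 SD effect reads as 0.5 - 0.2 = 0.3 SD within arm, and still as 0.5 SD between arms.

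**3. What the 4-month contrast can detect.** Baseline-adjusted SE = sqrt(2(1 - r^2)/n) = sqrt(2 x 0.64/60) = 0.146. Starting from a 0.5 SD effect, power is 92% if it is fully sustained, 72% if 75% remains (0.375 SD), and the nominal 5% if it is gone. For the sustained case the range is 84% to 99.5% for r from 0.4 to 0.8, 86% with 48 per arm, and 53% if the effect is 0.3 SD.

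**4. Trajectory model with all four visits and no exposure term.** Write the benefit difference (immediate minus delayed) at 0, 2, 4 and 6 months in units of d, with the delayed arm gaining d by 6 months. Use centred time (-3, -1, 1, 3; sum of squares 20).

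- Fully sustained (0, 1, 1, 0): linear slope (-1 + 1)/20 = 0; quadratic (0 - 1 - 1 + 0)/16 = -0.125d.
- Gone by 4 months (0, 1, 0, -1): linear slope (-1 - 3)/20 = -0.2d per month; quadratic (0 - 1 - 0 - 1)/16 = -0.125d.

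At d = 0.5 the linear term alone rejects 5% of the time when benefit is sustained and 97% when it is gone. The quadratic term is the same in both cases and rejects 99% of the time. For the sustained case the joint linear-plus-quadratic test rejects 98% and the 3-df categorical-time test 96%. On visits 0, 2 and 4 only, the sustained case gives a linear slope of (2 x 1)/8 = 0.25d per month.

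**5. Whether the 4-month contrast exists.** Under Study Design with a 4-month wait, the immediate arm is seen at 0, 3 and 6 months and the delayed arm at 0, about 4, 7 and 10. The arms share no visit after baseline. Neither the 0-2 month primary contrast nor a 4-month contrast could then be run as described.

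**The case against.** **The within-arm reading is an inference.** The mixed model is first introduced as a between-group model, and the persistence sentence does not confine its comparisons to one arm. A two-arm fit could yield a 4-month contrast. This stands: the plan does not exclude that contrast, it only fails to name it. But a sentence that opens from the immediate group's visits and speaks of time effects and pairwise time points does not commit anyone to it.

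**Drift is already in view.** The plan does set the delayed arm's untreated data aside to look for placebo effects and decline. A reader might infer that the plan expects drift. It does not; it proposes to check whether there is any. What is missing is the subtraction.

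**The trajectory harm can be overstated.** A reader might infer that a fully sustained benefit would be reported as no effect. That requires four things together: the 6-month visit enters, there is no exposure term, time is continuous, and the linear term is read alone. The plan states none of the four conditions, and the non-linear terms it does plan would detect a difference (step 4). What stands is narrower: a significant group-by-time term would not by itself show whether benefit lasted.

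**The free comparison depends on the schedule.** This stands. Recruitment also ties start dates to scheduling at each agency, so even on 2/4/6 months the delayed arm's untreated status at 4 months has to be secured.

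**Conclusion.** The point holds as a conditional improvement to a secondary analysis. If the 2/4/6-month schedule is the operative one, persistence should rest on the randomized 4-month contrast and not on change within the immediate arm. With a modest 0.2 SD shared drift and no Savvy effect, the within-arm route gives a significant 0-4 month change about 24% or 17% of the time after Sidak for 3 or 6 pairs, against about 5% between arms. These figures rest on the assumed arm size, correlation, drift and number of pairs, and ignore clustering and dropout.

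A reader might infer that the efficacy test itself is compromised. The documents do not support that on this schedule: the 0-2 month contrast is randomized, states its visits and is unaffected. Persistence is a clause in the analysis plan, not a named Aim 3 outcome. Leaving the trajectory model's visits unlisted is, taken alone, missing detail. Severity is low to moderate.

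**What to change.** 1. Reconcile the interview schedule: Study Design and Recruitment against Setting and location, Field Methods and Plans for analysis.
2. If 2/4/6 months is operative, keep the 0-2 month contrast primary. Add the 4-month between-arm contrast as the test of persistence, baseline-adjusted and taken from the mixed model with categorical time. Use visits made before the delayed arm starts Savvy.
3. Label the immediate arm's 6-month change as uncontrolled.
4. List the visits in each model. For the between-arm trajectory model, either restrict it to 0, 2 and 4 months, or include 6 months with a term for the delayed arm's Savvy exposure, such as a time-varying indicator. Either is defensible.

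On the 2/4/6-month schedule the cost is SAP wording only, with no new interviews or participants. If the Study Design and Recruitment schedule is operative, neither arm has a 2-month interview and the immediate arm has none at 4 months, so the primary contrast must be restated along with this one.

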certification and an accompanying performance fidelity monitoring process. This phase will occupy the project's first 14 months and will involve no human subject research participation. Phases 2 and 3 of the study involve human subject research participation. All human subject research activities will be conducted by members of the Emory study team, identified above; no non-Emory study team members will have any contact with Phase 2 and 3 research subjects. The second project phase, which will begin in project month 9 and extend through project month 24, will involve a formative evaluation of the prototype web-based system. In this phase, administrators and interventionists-in-training from 3 collaborating organizations and 36 informal dementia caregivers from these organizations will participate as research subjects. The administrators and interventionists will take part in semi-structured evaluation interviews; the caregivers will be asked to participate in Savvy programs offered by the newly-trained interventionists and they (the caregivers) will be asked to complete pre- and post-Savvy participation interviews both about the effect of the program on them and about their evaluation of the program. Phase 2 results will enable us to revise the interventionist training system, as needed. Once the system is deemed ready, we will, in phase 3, conduct a field test of the system implemented in six culturally and/or organizationally diverse sponsoring agencies. This test will again involve administrators, interventionists-in-training, and 120 dementia caregivers from participating organizations as research participants. The Aim 3 test will principally assess the effectiveness of the system in training interventionists who maintain fidelity to Savvy core principles; this portion of the test involves semi-structured interviews with the administrators, interventionists and a sample of caregivers. The test will also assess the preliminary efficacy of programs led by system-trained interventionists in producing anticipated outcomes in caregiver participants – reduced depression and burden and enhanced caregiving mastery. In this portion of the test, caregivers will be randomly chosen to participate immediately in a Savvy program offered by one of the organization's newly trained interventionists or to participate after a waiting period of 4 months. Those who

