take part in the program immediately will be asked to take part in 3 interviews (baseline and then 3 and 6 months after the start of the program. Those in the delayed start group will be asked to take part in 4 interviews (baseline (at the point of signing up for a later program), immediately prior to the beginning of the program and then 3 and 6 months after the start of the program. Standard instruments will be used to assess burden, mood (anxiety and depression), caregiving confidence and mastery, and care recipient well-being.

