addition to sponsor-based debriefings, the semi-structured interviews we will conduct with the interventionists during the Aim 2 and Aim 3 studies will also provide a linkage for them to the overall study and will, hopefully, provide them with a sense of ownership in the developing system.

*Caregivers.* It will only be family caregivers who will be part of the clinical trial component of this study (in Aims 2 and 3). Recruitment into the studies will be through referral from the sponsoring organizations. Each organization will recruit caregivers to take part in Savvy programs provided by interventionists trained in the system we are developing. We will provide organizations with materials they can use to announce Savvy and the studies; we will encourage the organizations to insert these materials into their own standard informational templates (i.e., standard logo and graphics). For caregivers willing to do so, their contact information will be provided to the Emory study team. We will arrange a phone or video call with each during which we will explain the study (Aim 2 or Aim 3 – a caregiver will not be able to take part in both), explain eligibility criteria, and seek informed consent (verbally) for participation. We do not anticipate attrition to be a problem in the Aim 2 study; research contact, following consent, will occur over a very brief period of time. All who consent to the Aim 2 study will take part immediately in a Savvy program and in an on-line survey and (for some) in-person interview conducted by phone or video right after the program. Prolonged retention will be more of a challenge in the Aim 3 study. Those taking part will enter a Savvy program either immediately or after a delay based on scheduling at the individual agencies. For those taking part immediately a series of 3 phone or video interviews will bracket their Savvy participation (at baseline then at 3 and 6 months following baseline. For those with a delayed start, we will conduct 4 interviews (upon sign up, immediately prior to the start of the program and then 3 and 6 months after program completion). To foster engagement with the project, we will prepare and distribute to participants a monthly project newsletter,

featuring tips on exercise and healthy eating and profiles of the study team. We will also send birthday and seasonal holiday cards, as appropriate.

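### The Aim 3 caregiver interview schedules contradict each other, and two of them contain no month-2 interview for the primary 0-to-2-month comparison

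*Combined protocol and SAP*

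**What the plan says.** The document describes the Aim 3 caregiver interviews in five places.

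- **Section 10 (Plans for analysis)** works on months 0, 2, 4 and 6. For the primary effect, "the Immediate group will be compared to the waitlist delay group, using the first 2 time points (0m-2m". A combined before/after analysis takes the delayed arm's "2 time points before and after beginning Savvy (4m-6m". A longitudinal model relies on the statement that "the immediate group will have 3 post-intervention measurements (2m-4m-6m". A placebo/decline check uses "time points for the delay group (0m-2m-4m".
- **Field Methods** sets follow-up at months 2, 4 and 6 after random assignment, without distinguishing the arms.
- **Setting and location** gives every participant four interviews and names no months.
- **Section 5, design overview**, delays one arm ("to participate after a waiting period of 4 months") and gives the immediate arm "3 interviews (baseline and then 3 and 6 months after the start of the program". The delayed arm has four: one at sign-up, then "immediately prior to the beginning of the program and then 3 and 6 months after the start of the program".
- **Recruitment (Caregivers)** gives the immediate arm three interviews, "at baseline then at 3 and 6 months following baseline". The delayed arm has four, but the last two are counted from the end of the program, not its start. This section also leaves the length of the delay to each agency's calendar.

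**The concern.** These are three different schedules for the same caregivers. They differ in the immediate arm's number of interviews (three or four), in the months, and in the clock (baseline, program start or program completion). Nothing says which one staff should follow.

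Only the Field Methods schedule supplies the visits that Section 10 analyses. If interviews are booked by the design overview or by Recruitment, the primary contrast, the delayed arm's 4-to-6-month pair and its 0-2-4-month run-in cannot be computed as written. A month-2 interview that was never held cannot be recovered. Any substitute would compare unequal intervals or depend on a time trajectory assumed in the mixed model.

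The caregiver result is labelled preliminary, but this is its stated primary comparison. Section 10 also uses caregiver outcomes to judge whether the training system is ready for a Stage III or IV trial.

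**Working it through.** **Inputs.** The wait is W = 4 months (design overview, Setting and location, Field Methods). Two quantities are not in the documents: d, the lag from baseline to the start of the immediate program, and L, the program length. I take d from 0 to 1 month and L from 0 to 2 months as assumptions.

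**The plan's own figure.** Section 10 counts three post-intervention measurements in the immediate arm. Field Methods reproduces this: baseline plus {2, 4, 6} gives three. The design overview and Recruitment give two.

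**Schedules in months from baseline.**

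| Source | Immediate arm | Delayed arm |
|---|---|---|
| Section 10 and Field Methods | 0, 2, 4, 6 | 0, 2, 4, 6 |
| Design overview | 0, 3+d, 6+d | 0, W, W+3, W+6 = 0, 4, 7, 10 |
| Recruitment, with W = 4 | 0, 3, 6 | 0, 4, 7+L, 10+L |

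For L from 0 to 2, the last two delayed-arm interviews under Recruitment fall at months 7 to 9 and 10 to 12.

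**Coverage of Section 10.** Its analyses together use 2 arms × 4 months = 8 cells. Under the design overview with d = 0, or under Recruitment with W = 4, the cells collected are immediate {0, 6} and delayed {0, 4}, so 4 of 8. By analysis:

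- Primary contrast, month-2 cells: 0 of 2.
- Delayed arm, months 4 and 6: 1 of 2.
- Immediate arm, months 2, 4 and 6: 1 of 3.
- Delayed arm, months 0, 2 and 4: 2 of 3.
- Visits shared by both arms after baseline and before crossover: none. The nearest substitute sets a 0-to-3-month change against a 0-to-4-month change.

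**Sensitivity to the unstated quantities.**

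- *Lag in the immediate arm only (design overview).* At d = 0.5 the immediate arm is {0, 3.5, 6.5}: 3 of 8 cells and no shared visit. At d = 1 it is {0, 4, 7}: 4 of 8 cells and a shared visit at month 4.
- *Lag in both arms*, for instance if it arises while the cohort of 20 is forming. At d = 1 the arms are {0, 4, 7} and {0, 5, 8, 11}: 3 of 8 cells and no shared visit.
- *A different wait*, which Recruitment's agency-set delay would allow. W = 3 creates a shared month-3 visit. W = 2 puts the delayed arm's pre-program interview at month 2.

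In every case the immediate arm's first follow-up is at month 3 or later. Its month-2 cell is therefore always empty, and the 0-to-2-month contrast fails whatever values d, W and L take.

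**The case against.** The strongest reply is that the document already contains a schedule that works. Field Methods describes assignment and follow-up together, its months are those of Section 10, and the count of four in Setting and location fits. On that view the other two descriptions are loose narrative, and the task is editing rather than rescuing an analysis. It is true that the harm depends on which text staff follow. But the design overview is where a reader would look first, a second section repeats the 3- and 6-month pattern, and nothing ranks the descriptions.

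Several narrower points stand:

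- Setting and location gives only a count. It conflicts with the design overview and Recruitment for the immediate arm (four against three) and agrees with them for the delayed arm.
- The 4-of-8 count, and the absence of a shared visit, depend on the 4-month wait and the assumed lag. They are illustrations.
- Each arm would still have two first time points, so a weaker contrast of roughly 0 to 3 against 0 to 4 months could be run. It is not the one specified.

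One could also say that the mixed model accommodates missing data. Section 10 relies on that for missingness due mainly to attrition. It does not help when a visit was never planned: there would be no month-2 data in the immediate arm, and an estimate there would come from the assumed trajectory.

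**Conclusion.** The concern holds. The current text gives three incompatible schedules with no statement of precedence, and two of them cannot supply the primary comparison as specified. The firm result, free of assumptions about lag, wait or program length, is that neither of those two schedules contains a month-2 interview in the immediate arm. With the 4-month wait the delayed arm has none either. The wider loss (4 of 8 cells, no shared visit before crossover) rests on that wait and, for the design overview, on the immediate program starting at baseline. This should be corrected before interviews are booked.

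**What to change.** Adopt one interview schedule, timed from randomization, and state it identically in the design overview, Setting and location, Recruitment, Field Methods and Section 10. Timing from randomization is a recommendation, not something the documents require. The amendment should:

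- give both arms common visits before crossover. Section 10 as written can be run only with interviews at months 0, 2, 4 and 6 in both arms, and with the delayed arm's month-4 interview held before its program begins;
- reconcile the agency-set delay in Recruitment with the 4-month wait stated elsewhere;
- say whether later delayed-arm interviews are kept and, if so, whether they run from program start or program completion;
- state the program length, so that month 2 can be confirmed as a post-intervention visit.

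**Cost.** Against Field Methods and Setting and location, only wording changes. Against the design overview, assuming 60 per arm and no attrition:

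- Interviews rise from 60×3 + 60×4 = 420 to 120×4 = 480. The extra 60 cost 60 × $25 = $1,500 at the Section 8 honorarium, and 60 to 90 hours at the 1 to 1.5 hours per interview in Field Methods.
- The delayed arm loses its two later follow-ups, leaving one interview about 2 months after its program starts. Keeping both as additional visits brings the total to 60×4 + 60×6 = 600: a further 120 interviews, $3,000 and 120 to 180 hours.

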## **Data Management**

Data will be entered at the time of each interview directly into the dedicated project tablet computer and saved on Emory's secure REDCap platform. All data entry screens are set up in REDCap and, where possible, include data delimiters (i.e., skip patterns, valid range limits) to ensure correctness and minimize missing data. Data will be exported weekly and analyzed for data cleaning and verification. Upon completion of each cohort data-gathering point, all data will be merged for scale computation, aggregation, and analysis. In preliminary analyses, descriptive statistics and frequency distributions will be examined to identify outliers and ensure integrity of merged files. For all multi-item scales, internal consistency will be examined using Cronbach's alpha and associated statistics (e.g., item-total correlations, alpha if item deleted).

Preliminary analyses will examine baseline differences among completers and non-completers and by study arm (immediate/delayed) as a randomization check using 2-group comparison tests (t-tests and non-parametric equivalent tests for continuous variables (normally or non-normally distributed) and Chi-Square tests for categorical variables). The association of predisposing factors (demographics, CG history, relationship and care recipient status at baseline) at baseline data with changes in outcomes over time will be examined to identify significant covariates. Where significant associations with baseline measures are detected, these potential confounders will be controlled for in subsequent analyses using covariate model adjustments.

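### The primary 0m-2m contrast has no unconditional adjustment for the 0m outcome; always adjusting would be a nearly costless gain in precision on the 0/2/4/6-month schedule

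*Combined protocol and SAP*

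**What the plan says.** Section 10 (Plans for analysis) of the combined protocol and SAP sets the model: "Multi-level mixed effects models (MLM) with random (participant) and fixed (cohort) effects will be employed", with the focus on group by time. For the primary effect, "the Immediate group will be compared to the waitlist delay group, using the first 2 time points (0m-2m) to test for differences" between the two groups' changes. No 0m outcome covariate and no common 0m mean is specified for this contrast.

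Two other passages could bring in a baseline score.

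- Section 10 next describes a combined analysis that pools the immediate group's 0m-2m with the delayed group's 4m-6m. It continues: "If there are significant differences between the 2 groups at the time point immediately prior to receipt of the intervention", these effects are to be included and "adjusted for a final analysis of covariance (ANCOVA) model for these change scores".
- Data Management (section 9) relates "predisposing factors (demographics, CG history, relationship and care recipient status at baseline" to changes in outcomes, and then says: "Where significant associations with baseline measures are detected, these potential confounders will be controlled for in subsequent analyses".

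On timing, section 10 and Field Methods place interviews at 2, 4 and 6 months. The four interviews per participant under Setting and location fit 0/2/4/6 months. Study Design (section 5) gives the immediate arm interviews at baseline, 3 and 6 months. After its sign-up interview, the delayed arm is seen "immediately prior to the beginning of the program and then 3 and 6 months after the start of the program". Recruitment gives the delayed arm interviews "upon sign up, immediately prior to the start of the program and then 3 and 6 months after program completion".

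**The concern.** In a randomised comparison with a baseline and one follow-up, a change score gives the baseline a fixed weight of one. Regression on the baseline uses the weight that the data support. Unless the correlation is very close to 1, the change score is the noisier estimator. The 0m scores are collected anyway, so precision that is already paid for is left unused.

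The plan also does not settle whether the 0m score enters the primary model. Two analysts who follow sections 9 and 10 faithfully could report different standard errors for the main efficacy result. That result counts for something: the last part of section 10 uses improvement in caregivers as evidence that system-trained interventionists can deliver the program, and the trial has only 120 caregivers.

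**Working it through.** **Inputs from the documents.** N = 6 sponsors x 20 = 120 (Goals/Aims, Aim 3); random assignment to immediate or delayed start (Field Methods); 5% level (section 10).

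**Assumptions, because the documents are silent.** Equal allocation (60 per arm), a two-sided test, equal SDs at 0m and 2m, independent participants, and 0m-2m correlation rho from 0.5 to 0.8. The plan states no effect size, SD or power, so there is no figure of its own to reproduce.

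**Step 1: what the planned contrast is.** With two complete time points, the group-by-time term of a random-intercept model is the difference in mean change. On one simulated data set (without cohorts), the mixed model and the change-score comparison gave the same result: estimate 0.581, SE 0.140. ANCOVA on the same data had SE 0.126. A cohort main effect is constant over time and cancels from 2m minus 0m.

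**Step 2: variance.** Per participant, in SD² units:
- change score: 2(1 - rho)
- ANCOVA: 1 - rho²
- ratio ANCOVA/change: (1 + rho)/2

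**Step 3: detectable effect at 80% power.** This is 2.80 x sqrt(variance x 2/60).

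| rho | change variance | ANCOVA variance | ratio | detectable, change (SD) | detectable, ANCOVA (SD) |
|---|---|---|---|---|---|
| 0.5 | 1.00 | 0.75 | 0.75 | 0.51 | 0.44 |
| 0.6 | 0.80 | 0.64 | 0.80 | 0.46 | 0.41 |
| 0.7 | 0.60 | 0.51 | 0.85 | 0.40 | 0.37 |
| 0.8 | 0.40 | 0.36 | 0.90 | 0.32 | 0.31 |

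At rho 0.5, 120 caregivers with ANCOVA are worth 120/0.75 = 160 with change scores; at rho 0.8, 120/0.90 = 133. The price is one degree of freedom, and break-even comes only at rho of about 0.98.

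**Step 4: missing 2m data.** Assume 20% missing at 2m, so 60 at 0m and 48 at 2m per arm. Section 10 keeps all available data, so the comparator is the mixed model on everyone, with per-arm variance (1 - rho²)/48 + (1 - rho)²/60. Under ANCOVA it is (1 - rho²)/48.
- rho 0.5: 0.01563 + 0.00417 = 0.01979 against 0.01563. Ratio 0.79; detectable 0.56 against 0.50 SD.
- rho 0.8: 0.00750 + 0.00067 = 0.00817 against 0.00750. Ratio 0.92; detectable 0.36 against 0.34 SD.

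**Step 5: wide reading of the Data Management screen.** Suppose the 0m score counts as a baseline measure. Its correlation with change is -sqrt((1 - rho)/2), from -0.50 (rho 0.5) to -0.32 (rho 0.8). In 40,000 simulated null trials per rho it passed a 5% screen in 100, 99.9, 99.3 and 94.6% of trials (rho 0.5, 0.6, 0.7, 0.8). Entered as an ANCOVA covariate when it passed, it gave variance ratios of 0.76, 0.81, 0.86 and 0.90, which is practically the whole gain.

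**Step 6: validity of the planned test.** In the same simulations the change score's type I error was 4.8 to 5.3%.

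**The case against.** The strongest reply is that the plan does provide for baseline adjustment. Data Management promises to control for baseline measures associated with change, and step 5 shows that the 0m score would nearly always qualify. On that reading the loss is close to zero. This stands in part: a reader might infer that the plan has no prespecified adjustment at all, and the documents do not support that. But the list being screened names demographics, caregiving history, relationship and care recipient status, and not the caregiver's own score. The wide reading is possible, not clear. Even then, inclusion depends on a test in the trial data, and the plan does not say how the score would enter the model.

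A second reply points to the ANCOVA in section 10. On its face that sentence belongs to the combined analysis, where the delayed arm's pre-intervention point is 4m. If it were carried over to the primary contrast, a 5% test of the 0m difference would be significant in only about 5% of randomised trials. A reader might go on to infer that the rule costs precision in the combined analysis too. Nothing calculated here addresses that analysis, and no such claim is made.

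A third reply concerns dropout. Comparing completers only, 48 per arm, would give 0.57 against 0.50 SD at rho 0.5. That overstates the gain, because section 10 uses all available data; the figures in step 4 are the right ones.

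Finally, materiality is modest. Rho is assumed, no stated power target is missed, and Study Design says Aim 3 principally assesses the training system, with caregiver efficacy preliminary. All of this stands. It limits the weight of the point but gives no reason to prefer the less precise analysis.

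**Conclusion.** The point holds as an optional, nearly free improvement. The primary between-arm contrast is in effect a change-score comparison without unconditional adjustment for the 0m outcome.

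A reader might infer bias or an inflated error rate. Neither follows: under randomisation the planned contrast is unbiased and its type I error is correct.

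The size depends on a correlation that the documents do not give. Over an assumed 0.5 to 0.8, the adjusted variance is 0.75 to 0.90 of the planned one with complete data, and 0.79 to 0.92 with an assumed 20% missing at 2m. It is practically no improvement if the Data Management screen is read widely and applied as ANCOVA. The figures further assume equal allocation, equal SDs, independent participants and a 0m interview completed before allocation is known, an order that the documents do not state outright.

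The point applies only on the 0/2/4/6-month schedule.

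**What to change.** First reconcile the visit schedule. Field Methods and section 10 support a 2-month interview in both arms. Taking the immediate program to start at month 0 and the delayed one at month 4, Study Design implies about 0/3/6 months for the immediate arm and 0/4/7/10 for the delayed arm. Recruitment counts the delayed arm's last two interviews from program completion instead. Neither of these gives the arms a shared early follow-up.

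Then, in section 10, for the primary between-arm contrast:

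- Always adjust for the 0m value of each outcome analysed. Use either ANCOVA of the 2m score on the 0m score, or a mixed model of both time points with one common 0m mean across arms. The second keeps all available data and stays within the planned framework.
- Retain the cohort fixed effect.
- State that this adjustment does not depend on any baseline significance test, neither the Data Management screen nor the conditional ANCOVA sentence in section 10.

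On the 0/2/4/6-month schedule this is a change of wording that costs one degree of freedom and needs no extra visits, participants or data. If another schedule is adopted, a common first follow-up has to exist before the adjustment can be specified, and the change is then more than wording.
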